#### **12.2.10.1. Data Monitoring Committee**

An independent data monitoring committee (DMC) will review unblinded safety data during this trial. The DMC will consist of suitably qualified people who are external to Lilly. This DMC will follow the rules defined in the DMC charter, focusing on the safety results for this antibody.

The DMC will be authorized to review unblinded results of analyses by treatment group prior to Week 60, including study discontinuation data, SAEs, clinical laboratory data, etc. The DMC may recommend continuation of the study, as designed; temporary suspension of enrollment; or the discontinuation of a particular dose regimen or the entire study. While the DMC may request to review efficacy data to investigate the benefit/risk relationship in the context of safety observations for ongoing patients in the study, no information regarding efficacy will be communicated. The study will not be stopped for positive efficacy results nor will it be stopped for futility; hence, no alpha is spent. Details of the DMC, including its operating characteristics, will be documented in a DMC charter.

## 13. Informed Consent, Ethical Review, and Regulatory Considerations

### 13.1. Informed Consent

The investigator is responsible for ensuring that the patient understands the potential risks and benefits of participating in the study, including answering any questions the patient may have throughout the study and sharing in a timely manner any new information that may be relevant to the patient's willingness to continue his or her participation in the trial.

The ICF will be used to explain the potential risks and benefits of study participation to the patient in simple terms before the patient is entered into the study, and to document that the patient is satisfied with his or her understanding of the risks and benefits of participating in the study and desires to participate in the study.

The investigator is responsible for ensuring that informed consent is given by each patient or legal representative. This includes obtaining the appropriate signatures and dates on the ICF prior to the performance of any protocol procedures and prior to the administration of investigational product.

As used in this protocol, the term "informed consent" includes all consent and assent given by patients or their legal representatives.

### 13.2. Ethical Review

Lilly or its representatives must approve all ICFs before they are submitted to the ERB and are used at clinical sites(s). All ICFs must be compliant with the ICH guideline on GCP.

Documentation of ERB approval of the protocol and the ICF must be provided to Lilly before the study may begin at the clinical site(s). The ERB(s) will review the protocol as required.

Any member of the ERB who is directly affiliated with this study as an investigator or as site personnel must abstain from the ERB's vote on the approval of the protocol.

The study site's ERB(s) should be provided with the following:

- the current IB or package labeling and updates during the course of the study
- ICF
- relevant curricula vitae

### 13.3. Regulatory Considerations

This study will be conducted in accordance with:

- 1) consensus ethics principles derived from international ethics guidelines, including the Declaration of Helsinki and Council for International Organizations of Medical Sciences (CIOMS) International Ethical Guidelines
- 2) the ICH GCP Guideline [E6]
- 3) applicable laws and regulations

The investigator or designee will promptly submit the protocol to applicable ERB(s).

All investigators are expected to comply with GCP and all applicable local clinical trial regulations.

All or some of the obligations of the sponsor will be assigned to a TPO.

An identification code assigned by the investigator to each patient will be used in lieu of the patient's name to protect the patient's identity when reporting AEs and/or other trial-related data.

### ***13.3.1. Protocol Signatures***

The sponsor's responsible medical officer will approve the protocol, confirming that, to the best of his or her knowledge, the protocol accurately describes the planned design and conduct of the study.

After reading the protocol, each principal investigator will sign the protocol signature page and send a copy of the signed page to a Lilly representative.

### ***13.3.2. Final Report Signature***

The clinical study report coordinating investigator will sign the final clinical study report for this study, indicating agreement that, to the best of his or her knowledge, the report accurately describes the conduct and results of the study.

The clinical study report coordinating investigator will be selected by the sponsor. If this investigator is unable to fulfill this function, another investigator will be chosen by Lilly to serve as the clinical study report coordinating investigator.

The sponsor's responsible medical officer will approve the final clinical study report for this study, confirming that, to the best of his or her knowledge, the report accurately describes the conduct and results of the study.

## **Attachment 1. Protocol RHBH Study Schedule**

---

**Study Schedule, Protocol I1F-MC-RHBH**

	Screening		Baseline	Induction Dosing Period (Period 2)					Maintenance Dosing Period (Period 3)		
	V1	V1A	V2	V3	V4	V5	V6	V7	V8	V9	V10
Study Week			W0	W1	W2	W4	W8	W12	W16	W20	W24
Study Days	-30 to -4d	2-3d post V1	0	7±2d	14±2d	28±2d	56±4d	84±4d	112±7d	140±7d	168±7d
Informed consent	×										
Complete medical history	×										
Demographics a	×										
Physical exam b	×							×			×
Weight c			×					×			×
Waist circumference			×					×			×
Height			×								
Habits d			×								×
Chest X-ray	× e										
Body temperature			×								
Inclusion/Exclusion criteria f	×		×								
Randomization			×					×			
Concomitant medications	×		×	×	×	×	×	×	×	×	×
Vital signs (BP and pulse)	×		× g	×	×	×	×	× g	×	×	×
Review preexisting conditions	×										
AE			×	×	×	×	×	×	×	×	×
Administer IP			Blinded 160mg LY (2 injections 80mg each) or LY placebo (2 injections) g,h		Blinded 80mg LY Q2W*, 80mg LY Q4W*, or LY placebo Q2W* h (1 injection given Q2W)			Blinded 80mg LY Q4W**, or LY placebo Q4W** ij (2 injections)	Blinded 80mg LY Q4W** or LY placebo Q4W** ij (1 injection Q4W)		
Dispense IP			×		×	×	×	×	×	×	×

	Screening		Baseline	Induction Dosing Period (Period 2)					Maintenance Dosing Period (Period 3)		
	V1	V1A	V2	V3	V4	V5	V6	V7	V8	V9	V10
Study Week			W0	W1	W2	W4	W8	W12	W16	W20	W24
Study Days	-30 to -4d	2-3d post V1	0	7±2d	14±2d	28±2d	56±4d	84±4d	112±7d	140±7d	168±7d
IP compliance			×		×	×	×	×	×	×	×
Dispense Study Drug Administration Log k			×		×	×	×	×	×	×	×
Collect, review, and enter data from Study Drug Administration Log			×		×	×	×	×	×	×	×
Clinical Efficacy/ Health Outcomes											
sPGA	×		×	×	×	×	×	×	×	×	×
PASI	×		×	×	×	×	×	×	×	×	×
BSA	×		×	×	×	×	×	×	×	×	×
NAPSI z			×	×	×	×	×	×	×	×	×
PSSI z			×	×	×	×	×	×	×	×	×
PPASI z			×	×	×	×	×	×	×	×	×
Itch NRS			×	×	×	×	×	×	×	×	×
DLQI l			×		×	×		×			×
QIDS-SR16	×		×					×			×
C-SSRS x			×	×	×	×	×	×	×	×	×
Self-Harm Supplement Form			×	×	×	×	×	×	×	×	×
Joint Pain VAS z			×	×	×	×	×	×	×	×	×
SF-36			×					×			×
Patient's Global Assessment of Disease severity			×	×	×	×	×	×	×	×	×
Laboratory Tests											
Administer PPD/QuantiFERON ® -TB Gold/ T-SPOT ® .TB m	×										

Visit No (V)	Screening		Baseline	Induction Dosing Period (Period 2)					Maintenance Dosing Period (Period 3)		
	V1	V1A	V2	V3	V4	V5	V6	V7	V8	V9	V10
Study Week			W0	W1	W2	W4	W8	W12	W16	W20	W24
Study Days	-30 to -4d	2-3d post V1	0	7±2d	14±2d	28±2d	56±4d	84±4d	112±7d	140±7d	168±7d
Read PPD		x									
ECGs n	x										
FSH o	x										
HIV/HCV	x										
HBV p,q	x		x					x			x
Serum pregnancy test r	x										
Urine pregnancy test r			x			x	x	x	x	x	x
Serum chemistry	x		x	x	x	x	x	x	x	x	x
Lipase/Amylase	x		x					x			
Lipid panel s	x		x			x		x			x
Advanced lipid profile			x					x			
Hematology	x		x	x	x	x	x	x	x	x	x
PTT and INR	x		x					x			
Urinalysis	x		x			x		x			x
TSH and Free T4	x										
IgA, IgG, IgM	x		x			x		x			x
CRP			x	x	x	x	x	x			x
Cell flow cytometry panel (B, T, CD4+T, CD8+T, and NK Cells)			x			x		x			x
Immunogenicity testing t			x		x	x		x			x
PK sampling y			x		x	x		x			x

	Maintenance Dosing Period (Period 3)									Post Treatment Follow up u (Period 4)			
Visit No (V)	V11	V12	V13	V14	V15	V16	V17	V18	V19	V801	V802	V803 v	ETV w
Study Week	W28	W32	W36	W40	W44	W48	W52	W56	W60	LV+4 W	LV+12W	LV+24W	
Study Days	196± 7d	224± 7d	252± 7d	280± 7d	308± 7d	336± 7d	364± 7d	392± 7d	420±7 d	±4d	±4d	±4d	
Physical exam b									x				x
Weight c									x				x
Waist circumference									x				x
Habits d									x				x
Concomitant medications	x	x	x	x	x	x	x	x	x	x	x	x	x
Vital signs (BP and pulse)	x	x	x	x	x	x	x	x	x	x	x	x	x
AE	x	x	x	x	x	x	x	x	x	x	x	x	x
Administer IP	Blinded 80mg LY Q4W** or LY placebo Q4W** i.j (1 injection)												
Dispense IP	x	x	x	x	x	x	x	x	x				
IP compliance	x	x	x	x	x	x	x	x	x	x			x
Dispense Study Drug Administration Log k	x	x	x	x	x	x	x	x	x				
Collect, review, and enter data from Study Drug Administration Log	x	x	x	x	x	x	x	x	x	x			x
sPGA	x	x	x	x	x	x	x	x	x				x
PASI	x	x	x	x	x	x	x	x	x				x
BSA	x	x	x	x	x	x	x	x	x				x
NAPSI z	x	x	x	x	x	x	x	x	x				x
PSSI z	x	x	x	x	x	x	x	x	x				x
PPASI z	x	x	x	x	x	x	x	x	x				x
Itch NRS	x	x	x	x	x	x	x	x	x				x

	Maintenance Dosing Period (Period 3)									Post Treatment Follow up u (Period 4)			
Visit No (V)	V11	V12	V13	V14	V15	V16	V17	V18	V19	V801	V802	V803 v	ETV w
Study Week	W28	W32	W36	W40	W44	W48	W52	W56	W60	LV+4 W	LV+12W	LV+24W	
Study Days	196± 7d	224± 7d	252± 7d	280± 7d	308± 7d	336± 7d	364± 7d	392± 7d	420±7 d	±4d	±4d	±4d	
DLQI 			x				x		x				x
QIDS-SR16			x				x		x				x
C-SSRS x	x	x	x	x	x	x	x	x	x	x	x	x	x
Self-Harm Supplement Form	x	x	x	x	x	x	x	x	x	x	x	x	x
Joint pain VAS z	x	x	x				x		x				x
SF-36			x				x		x				x
Patient's Global Assessment of Disease severity	x	x	x				x		x				x
ECGs n									x				x
HBV p,q			x			x			x		x		x
Urine pregnancy test r	x	x	x	x	x	x	x	x	x				x
Serum chemistry		x		x		x			x	x	x	x	x
Lipase/Amylase									x				x
Lipid panel s									x				x
Advanced lipid profile		x		x		x			x				x
Hematology		x		x		x			x	x	x	x	x
PTT and INR													
Urinalysis		x		x		x			x				x
TSH and Free T4													
IgA, IgG, IgM			x			x			x				x
CRP			x			x			x				x
Cell flow cytometry panel (B, T, CD4+T, CD8+T,			x						x		x		x

	Maintenance Dosing Period (Period 3)									Post Treatment Follow up u (Period 4)			
Visit No (V)	V11	V12	V13	V14	V15	V16	V17	V18	V19	V801	V802	V803 v	ETV w
Study Week	W28	W32	W36	W40	W44	W48	W52	W56	W60	LV+4 W	LV+12W	LV+24W	
Study Days	196± 7d	224± 7d	252± 7d	280± 7d	308± 7d	336± 7d	364± 7d	392± 7d	420±7 d	±4d	±4d	±4d	
and NK Cells)													
Immunogenicity testing t			×						×		×		×
PK sampling y			×						×		×		×

**Abbreviations:** AE = adverse event; BP = blood pressure; BSA = body surface area; CRP = C-reactive protein; C-SSRS = Columbia-Suicide Severity Rating Scale; d = days; DLQI = Dermatology Life Quality Index; DNA = deoxyribonucleic acid; ECG = electrocardiogram; ETV or Early Term Visit = early termination visit; FSH = follicle stimulating hormone; HBV = hepatitis B virus; HCV = hepatitis C virus; HIV = human immunodeficiency virus; IgA = immunoglobulin A; IgG = immunoglobulin G; IgM = immunoglobulin M; INR = international normalized ratio; IP = investigational product; LV = last visit; NAPSI = Nail Psoriasis Severity Index; PASI = Psoriasis Area and Severity Index; PPASI = palmoplantar Psoriasis Area and Severity Index; PPD = purified protein derivative; Ps = psoriasis; PSSI = Psoriasis Scalp Severity Index; PTT = partial thromboplastin time; Q2W = every 2 weeks; Q4W = every 4 weeks; SC = subcutaneous; SF-36 = Medical Outcomes Study 36-Item Short Form Health Survey; sPGA = static Physician's Global Assessment; T4 = thyroxine; TB = tuberculosis; TSH = thyroid stimulating hormone; V = study visit; W = study week.

\* **Period 2:** 80 mg Q2W = A starting dose of 160 mg (Week 0) given as 2 SC injections followed by 80 mg given as 1 SC injection Q2W (Weeks 2, 4, 6, 8, and 10); 80 mg Q4W = A starting dose of 160 mg (Week 0) given as 2 SC injections followed by 80 mg given as 1 SC injection Q4W (Weeks 4 and 8). To maintain blinding, placebo is given as 1 SC injection at Weeks 2, 6, and 10; Placebo = Placebo (Week 0) given as 2 SC injections followed by placebo Q2W (Weeks 2, 4, 6, 8, and 10). To maintain the study blind, all patients will receive 2 SC doses of investigational product at Week 0 (Visit 2) and 1 SC dose Q2W from Week 2 (Visit 4) through Week 10.

\*\* **Period 3:** 80 mg Q4W = A dose of 80 mg given as 1 SC injection + a placebo injection at (Week 12); 80 mg given as 1 SC injection Q4W thereafter.; Placebo = Placebo given as 2 SC injections at Week 12 followed by placebo given as 1 SC injection Q4W thereafter. To maintain the study blind, all patients will receive 2 SC doses of investigational product at Week 12 (Visit 7) and 1 SC dose Q4W from Week 16 (Visit 8) through Week 56 (Week 60, no IP administration). Study visits will occur at least Q4W during Period 3; Refer to Section 7.1.3 for the treatment assignments for Responders, Non-Responders, and patients who relapse in Period 3.

- a Demographics includes recording of year of birth, gender, and ethnicity.
- b One complete physical examination (excluding pelvic, rectal, and breast examinations) will be performed at screening. All physical examinations throughout the study should include a symptom directed physical as well as examination of heart, lungs, abdomen, and visual examination of the skin.
- c Weight collection is also used for calculating creatinine clearance.
- d Habits include recording of caffeine, alcohol and tobacco consumption.
- e A chest x-ray will be taken at screening unless one has been obtained within the past 6 months (provided the x-ray and/or report are available for review).
- f Patients who test positive for latent TB at screening may be rescreened following appropriate treatment as described in Section 10.3.2.2. Additionally, patients who do not qualify at screening under Exclusion Criteria [28] (active or recent infection) or Exclusion Criteria [29] (body temperature  $\geq 38^{\circ}\text{C}$  [ $100.5^{\circ}\text{F}$ ]) may be rescreened (1 time) as described in Section 8.2.
- g At baseline (Week 0) and Week 12, BP and pulse should be measured prior to administration of the investigational product and again approximately 1 hour post administration. At Week 12, the injection of the investigational product will be administered by the patient or an authorized adult who has been trained at the clinical site.
- h In Period 2, dose regimens, training, and subsequent dosing will be performed as described in Section 9.1.
- i All patients will receive 2 SC doses of investigational product at Weeks 0 and 12 to maintain the double blind (Sections 7.1.2 and 7.1.3).
- j In Periods 3, dosing will be assigned as described in Section 7.1.3, with applicable procedures as described in Section 9.1.
- k Patients will record information in the Study Drug Administration Log, including the date, time, and location of administration of investigational product (for treatment compliance), syringe number, who administered the investigational product, and the reason if investigational product was not fully administered or not administered at all.

- l See Section 10.2.2 for detailed description of DLQI
- m See Section 10.3.2.2 for detailed description of QuantiFERON Gold TB / T-SPOT®.TB and PPD testing.
- n ECGs should be performed prior to injection of investigational product, as applicable.
- o FSH test performed for women  $\geq 40$  and  $< 60$  years of age who have had a cessation of menses for at least 12 months to confirm non-childbearing potential ( $\geq 40$  mIU/mL).
- p All patients will be tested for HBV panel at screening.
- q Patients that are HBcAb+ at screening, regardless of hepatitis B surface antibody (HBsAb) status, will have a serum HBV DNA tested by the central laboratory. Patients that are HBV DNA negative (undetectable) may be enrolled into the study with required HBV DNA monitoring every 3 months during treatment and 12 weeks after the last dose of ixekizumab.
- r To be performed for females of childbearing potential only. Predose urine pregnancy testing will be performed at scheduled visits from Week 4 (Visit 5) through Week 60 (Visit 19). Patients will undergo urine pregnancy test at the site on a monthly basis during periods between scheduled visits until Week 60. Patients with a positive pregnancy test will be discontinued from treatment and will no longer be administered investigational product (See Section 8.3.1.1).
- s Fasting lipid profile: patients should not eat or drink anything except water for 12 hours prior to test.
- t Immunogenicity samples may also be analyzed for ixekizumab serum concentration to facilitate in the interpretation of the immunogenicity data. In addition, a blood sample will be collected prior to administration of investigational product, when possible, for any patient who experiences a potential systemic allergic reaction /hypersensitivity during the study as judged by the investigator.
- u All patients receiving investigational product must enter into Period 4 and complete through Visit 802. Patients may be followed beyond Visit 802 for continued monitoring of their neutrophil counts.
- v This visit will only occur if a patient's neutrophil counts have not returned to the criteria defined in Section 7.1.4.1.
- w If a patient discontinues investigational product early, the patient will complete the ETV and then enter the Post-Treatment Follow-Up Period (Period 4).
- x A Self-Harm Follow-Up Form is to be completed for each discrete self-harm event identified on the C-SSRS and the Self-harm Supplement Form.
- y PK samples will be collected after ECG are performed, and prior to administration of investigational product, as applicable.
- z If the subject has nail psoriasis, scalp psoriasis, palmoplantar psoriasis, joint pain at baseline, then the NAPSI, PSSI, PPASI, joint pain VAS, respectively, will be administered at subsequent visits, as indicated in the Study Schedule.

---

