  - Time course of response to treatment as measured by change from baseline and percent improvement from baseline of PASI
  - Change from baseline in percent of BSA involvement of Ps
  - Incidence of disease rebound within 8 weeks (worsening of Ps severity over baseline sPGA score, *or* worsening of Ps severity over baseline PASI score by 125%, *or* change in Ps phenotype [for example, from plaque to pustular]) after re-randomization to placebo at Week 12
  - Time course of response to treatment as measured by the proportion of patients who maintain a PASI 75, PASI 90, and PASI 100
  - Change from baseline in NAPSI score in patients with baseline fingernail involvement
  - Change from baseline in PSSI score in patients with baseline scalp involvement

- Change from baseline in other health outcome endpoints: SF-36 PCS and MCS scores and patient's global assessment of disease severity
- Change from baseline in itching severity (Itch NRS) score
- Change from baseline on DLQI
- Change from baseline in PPASI and proportion of patients achieving at least a 50% improvement in PPASI score from baseline (PPASI 50), at least a 75% improvement in PPASI score from baseline (PPASI 75), and a 100% improvement in PPASI score from baseline (PPASI 100) in patients with baseline palmoplantar involvement
- To assess the efficacy of ixekizumab 80 mg Q4W following disease relapse after re-randomization to placebo treatment in the Maintenance Dosing Period by evaluating:
  - Proportion of patients who regain an sPGA (0, 1) within 12 weeks after ixekizumab retreatment
  - Proportion of patients who achieve a PASI 75, PASI 90, PASI 100 within 12 weeks after ixekizumab retreatment
- To assess the efficacy of ixekizumab 80 mg Q2W or 80 mg Q4W compared to placebo on joint pain at Week 12 and over the Induction Dosing Period, as well as at Week 60 and during the Maintenance Dosing Period in patients with an sPGA (0, 1) at Week 12 and were re-randomized, by evaluating change from baseline in joint pain (Joint Pain visual analog scale [VAS]) score in patients with psoriatic arthritis (PsA) at baseline
- To evaluate the potential development of anti-ixekizumab antibodies and its impact on patient safety and efficacy
- To measure ixekizumab exposure and assess the relationship between exposure and efficacy, and exposure and immunogenicity

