### **10.2.5. Joint Pain Visual Analog Scale (VAS) Psoriatic Arthritis**

Patients diagnosed with psoriatic arthritis at baseline will complete the Joint Pain VAS. The Joint Pain VAS is a patient-administered scale designed to measure current joint pain from PsA using a 100-mm horizontal VAS. Overall severity of a patient's joint pain from PsA is indicated by placing a single mark on the horizontal scale (0 = none; 100 = as severe as you can imagine).

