**12.2.6.3.1. Period 2 (Induction Dosing Period)**

Unless otherwise specified, the other secondary analyses during Period 2 will be based on the ITT population.

For all categorical efficacy variables that are collected at repeated visits, treatment group comparisons will be analyzed at each visit using the logistic regression model and Fisher's exact test described in Section 12.2.1.1 where appropriate. Missing data will be imputed using the NRI method described in Section 12.2.1.4.1.

For all continuous efficacy variables that are collected at repeated visits, treatment group comparisons will be analyzed at each visit using the MMRM model as described in Section 12.2.1.1 when appropriate. No imputation methods are applied to MMRM analysis.

Time to sPGA response (sPGA [0,1]) is defined as the number of days from initial randomization to the first visit at which the patient has an sPGA [0,1] during Period 2 (Induction Dosing Period). Time to PASI 75 response is defined as the number of days from initial randomization to the first visit at which the patient has met the PASI 75 criterion during Period 2 (Induction Dosing Period). For patients who discontinue early in Period 2 or who complete Period 2 without meeting criteria for response, the time-to-first response will be censored and defined as the number of days from initial randomization to the patient's last visit during Period 2. Time to first response for each treatment group in Period 2 will be estimated using the Kaplan-Meier product limit method. Treatment group comparisons will be performed using the log-rank test.

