- In section 6.4, added a listing for patient disposition from study and study treatment due to COVID-19, respectively.
- In section 6.5, added a listing of protocol deviations due to COVID-19.
- In section 6.10 [Table RHBH. 6.7](#), MMRM analysis for Joint Pain VAS change from baseline will be based on 'ITT population - patients with baseline psoriatic arthritis' instead of 'ITT population - patients with baseline Joint Pain VAS >0'. The change was made so the analysis is consistent with the objective in section 4.2.2

4. Study Objectives

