 - Change from baseline in percent of BSA involvement of Ps
 - Incidence of disease rebound within 8 weeks (worsening of Ps severity over baseline sPGA score, *or* worsening of Ps severity over baseline PASI score by 125%, *or* change in Ps phenotype [for example, from plaque to pustular]) after re-randomization to placebo at Week 12
 - Time course of response to treatment as measured by the proportion of patients who maintain a PASI 75, PASI 90, and PASI 100
 - Change from baseline in NAPSI score in patients with baseline fingernail involvement
 - Change from baseline in PSSI score in patients with baseline scalp involvement

- Change from baseline in other health outcome endpoints: SF-36 PCS and MCS scores and patient's global assessment of disease severity
- Change from baseline in itching severity (Itch NRS) score
- Change from baseline on DLQI
- Change from baseline in PPASI and proportion of patients achieving at least a 50% improvement in PPASI score from baseline (PPASI 50), at least a 75% improvement in PPASI score from baseline (PPASI 75), and a 100% improvement in PPASI score from baseline (PPASI 100) in patients with baseline palmoplantar involvement
- To assess the efficacy of ixekizumab 80 mg Q4W following disease relapse after re-randomization to placebo treatment in the Maintenance Dosing Period by evaluating:
 - Proportion of patients who regain an sPGA (0, 1) within 12 weeks after ixekizumab retreatment
 - Proportion of patients who achieve a PASI 75, PASI 90, PASI 100 within 12 weeks after ixekizumab retreatment
- To assess the efficacy of ixekizumab 80 mg Q2W or 80 mg Q4W compared to placebo on joint pain at Week 12 and over the Induction Dosing Period, as well as at Week 60 and during the Maintenance Dosing Period in patients with an sPGA (0, 1) at Week 12 and were re-randomized, by evaluating change from baseline in joint pain (Joint Pain visual analog scale [VAS]) score in patients with psoriatic arthritis (PsA) at baseline
- To evaluate the potential development of anti-ixekizumab antibodies and its impact on patients' safety and efficacy
- To measure ixekizumab exposure and assess the relationship between exposure and efficacy, and exposure and immunogenicity

5. Study Design

This section contains the summary of study design, the method of treatment assignment, and the sample size determination from the protocol for Study I1F-MC-RHBH.

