	Logistic regression analysis with NRI; Fisher's exact test with NRI	Maintenance Dosing Period Primary Population	IXE80Q2W/IXE80Q4W vs. IXE80Q2W/PBO, IXE80Q4W/IXE80Q4W vs. IXE80Q4W/PBO and IXE/IXE vs IXE/PBO at Week 60 and all other postbaseline visits in Period 3
DLQI total score change from baseline — Major secondary	MMRM; ANCOVA with LOCF	ITT population	IXE80Q2W & IXE80Q4W vs. PBO at Week 12 and all other post-baseline visits
	MMRM; ANCOVA with LOCF	Maintenance Dosing Period Primary Population	IXE80Q2W/IXE80Q4W vs. IXE80Q2W/PBO, IXE80Q4W/IXE80Q4W vs. IXE80Q4W/PBO and IXE/IXE vs IXE/PBO at Week 60 and all other postbaseline visits in Period 3
DLQI domain scores change from baseline			
36 item Short Form Health Survey (SF-36)			
SF-36 PCS, MCS, domain scores change from baseline	MMRM	ITT Population	IXE80Q2W & IXE80Q4W vs. PBO at Week 12 and all other post-baseline visits
	MMRM	Maintenance Dosing Period Primary Population	IXE80Q2W/IXE80Q4W vs. IXE80Q2W/PBO, IXE80Q4W/IXE80Q4W vs. IXE80Q4W/PBO and

Variable	Analysis Method (Sections 6.1 and 6.2)	Population (Section 6.1.1)	Comparison / Time Point
			IXE/IXE vs IXE/PBO at Week 60 and all other postbaseline visits in Period 3
Patient's Global Disease Assessment (PatGA)			
PatGA score change from baseline	MMRM	ITT Population	IXE80Q2W & IXE80Q4W vs. PBO at Week 12 and all other post-baseline visits
	MMRM	Maintenance Dosing Period Primary Population	IXE80Q2W/IXE80Q4W vs. IXE80Q2W/PBO, IXE80Q4W/IXE80Q4W vs. IXE80Q4W/PBO and IXE/IXE vs IXE/PBO at Week 60 and all other postbaseline visits in Period 3
Joint Pain VAS			
Joint Pain VAS change from baseline	MMRM	ITT population - patients with baseline psoriatic arthritis	IXE80Q2W & IXE80Q4W vs. PBO at Week 12 and all other post-baseline visits
	MMRM	Maintenance Dosing Period Primary Population - patients with baseline psoriatic arthritis	IXE80Q2W/IXE80Q4W vs. IXE80Q2W/PBO and IXE80Q4W/IXE80Q4W vs. IXE80Q4W/PBO at Week 60 and all other postbaseline visits in Period 3

Abbreviations: ANCOVA = analysis of covariance; DLQI = Dermatology Life Quality Index; ITT = intent-to-treat; LOCF = last observation carried forward; MMRM = mixed-effects model of repeated measures; NRI = nonresponder imputation; NRS = Numeric Rating Scale; VAS = visual analog scale.

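### Schedule footnote z ties the post-baseline Joint Pain VAS to joint pain at baseline, while Protocol Section 10.2.5, the objective and the SAP tie it to baseline psoriatic arthritis

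*Protocol*

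**What the plan says.** Four places define who is assessed or analysed on the Joint Pain VAS.

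- **Protocol Attachment 1, footnote z.** A single conditional sentence covers four instruments: nail, scalp and palmoplantar psoriasis trigger the first three, and joint pain triggers the VAS. It ends: "joint pain at baseline, then the NAPSI, PSSI, PPASI, joint pain VAS, respectively, will be administered at subsequent visits". PsA is not mentioned, and the footnote does not say how joint pain at baseline is to be established.
- **Protocol Section 10.2.5.** "Patients diagnosed with psoriatic arthritis at baseline will complete the Joint Pain VAS". There is no pain condition and no list of visits.
- **Objectives (Protocol Section 6.2.2; SAP Section 4.2.2).** The protocol objective is met "by evaluating change from baseline in joint pain (Joint Pain visual analog scale [VAS]) score in patients with psoriatic arthritis (PsA) at baseline". The SAP objective likewise specifies the "score in patients with psoriatic arthritis (PsA) at baseline".
- **SAP Table RHBH.6.7.** The Period 2 analysis set is "ITT population - patients with baseline psoriatic arthritis" and the Period 3 set is "Maintenance Dosing Period Primary Population - patients with baseline psoriatic arthritis". Both are analysed by MMRM.

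The SAP's revision history (Section 3) records that version 2 set the PsA population deliberately: "The change was made so the analysis is consistent with the objective in section 4.2.2".

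**The concern.** Joint pain and a diagnosis of PsA are not the same condition. A patient with PsA may have no joint pain on the day of the baseline visit, and a patient without PsA may have joint pain from another cause. A site that applies footnote z as written would stop the VAS after baseline in the first kind of patient, whom the SAP means to analyse. It would continue the VAS in the second kind, whom the SAP does not analyse.

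What is at stake is whether the analysed group matches its label. A result headed as patients with baseline PsA could in practice describe PsA patients who had joint pain at baseline. Pain-free patients start at or near 0 mm and cannot improve, so leaving them out would probably make the mean change look larger than in the full PsA group.

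**Working it through.** The plan gives no sample size, power or prevalence for this endpoint, so there is no figure to reproduce. The check is a comparison of texts, followed by an illustration of size.

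**Step 1. Which patients each rule covers after baseline**

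| Patient at baseline | Footnote z, read literally | Section 10.2.5 | SAP Table RHBH.6.7 |
|---|---|---|---|
| PsA, joint pain | VAS | VAS | analysed |
| PsA, no joint pain | not provided for | VAS | analysed |
| No PsA, joint pain | VAS | not provided for | not analysed |

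Section 10.2.5 agrees with the SAP in every row. Footnote z disagrees in the second and third.

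**Step 2. Which rule a site would apply.** Protocol Section 7.1 and the opening of Section 10 both send the reader to the Study Schedule for procedures and their timing. Section 10.2.5 names no visits, so footnote z is the only text on who is assessed at later visits. A site could reasonably follow it. The footnote's other three triggers agree with Sections 10.1.2.1 to 10.1.2.3; only the joint-pain trigger departs from its own section, which suggests a drafting slip.

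**Step 3. Whether the analysis could recover the missing patients.** It could not.
- SAP Table RHBH.6.6 sets change from baseline to missing when the observed value is missing.
- The protocol says of its Period 2 continuous efficacy analyses: "No imputation methods are applied to MMRM analysis". Protocol Section 12.2.6.4 uses the same MMRM for the health outcomes.
- SAP Table RHBH.6.7 lists MMRM alone for this endpoint. Adding LOCF would not help, because SAP Section 6.2.2 leaves out patients with no post-baseline observation.

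**Step 4. Illustration of size.** The 420 randomized patients come from Protocol Section 12.1. Both proportions are assumptions that are not in the documents.

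Patients without post-baseline VAS = 420 × (share with PsA) × (share of those pain-free at baseline)

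- Low end: 420 × 5% = 21; 21 × 10% = 2.1, about 2.
- High end: 420 × 20% = 84; 84 × 40% = 33.6, about 34.
- If sites follow Section 10.2.5: 0.

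**The case against.** The strongest reply is that Section 10.2.5 is itself a collection rule. It covers every patient with baseline PsA, and a site that follows it collects exactly what the SAP analyses. Footnote z is worded as a condition and does not say that other patients are excluded. It can also be read as shorthand: three psoriatic manifestations and then joint pain, for an instrument that Section 10.2.5 and SAP Table RHBH.6.6 define as measuring joint pain from PsA. SAP Table RHBH.6.3 likewise summarises the baseline VAS in patients with baseline PsA. No case report form rule is shown, so what sites were prompted to do is unknown.

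Much of this stands. A reader might infer that the PsA population is bound to lack data; the documents do not support that, because the loss arises only where the footnote is followed in place of Section 10.2.5. The reply does not remove the conflict. A condition placed on four instruments has little purpose unless it limits who is assessed, and the protocol does not say which of its two rules prevails.

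A reader might also infer a biased comparison of ixekizumab with placebo. That does not follow either. Joint pain at baseline is fixed before randomization, so in Period 2 selecting on it applies alike to all arms. It narrows the population described without by itself distorting the contrast. Missing new joint pain in pain-free patients would be a loss of information, but new joint pain is not an endpoint in either document.

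**Conclusion.** The inconsistency is real: footnote z conflicts with Protocol Section 10.2.5, the objective and SAP Table RHBH.6.7. Its consequence is conditional. If sites followed the footnote, PsA patients who were pain-free at baseline have no post-baseline VAS, and the MMRM describes a narrower group than its label says. If sites followed Section 10.2.5, nothing is lost.

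The number affected cannot be determined from the documents. The range in the working rests wholly on the two assumed proportions and on the footnote having been followed. Importance is low: the Joint Pain VAS is an other secondary endpoint outside the ten gatekept tests, with no multiplicity adjustment, and no primary or major secondary conclusion depends on it.

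**What to change.** Reword footnote z so that the Joint Pain VAS at later visits follows a diagnosis of PsA at baseline, as Section 10.2.5 already has it, and remind sites. This costs one phrase and a few more single-item questionnaires.

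Timing matters. The Protocol Synopsis planned the last patient visit for June 2020 and SAP version 2 was approved on 27 July 2020, so collection may already have ended and a new footnote would not recover past visits. In that case, report by treatment group how many baseline-PsA patients have a baseline VAS and how many have at least one post-baseline VAS, and state which trigger sites applied. If pain-free PsA patients turn out to be missing, label the analysed population as PsA patients with joint pain at baseline. The cost is one count and one table label.
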